9.3 POPULATIONS FOR ANALYSES

We will use the Intent-to-treat sample (ITT). The ITT sample will include all subjects randomized, where subjects will be classified by the OTU dose in which they are randomized, regardless of the dose received. For each interim analysis (e.g. RAR, interim assessment for efficacy and futility) the analysis population will be defined as all subjects who have been randomized \geq 4 weeks from the time of the data freeze; the final analysis will occur once all subjects have the opportunity to complete the final study visit (i.e. randomized \geq 26 weeks previously).

Secondary Aims Analysis. This study, in addition to identifying the optimal dose, offers the opportunity to explore the treatment effect in other important outcome domains using ICP, TIL scores and brain tissue PO2. These analyses will allow us to further support a go/no-go decision regarding a subsequent definitive efficacy trial. Based on our previous work, we anticipate brain tissue PO2 would have better power than ICP (Rockswold 2010, Rockswold 2013). Additionally, (1) the therapeutic intensity level (TIL) scores for controlling intracranial pressure (ICP) in hyperoxia-treated subjects will be compared to controls; and (2) in centers utilizing brain tissue PO2 monitoring, the level and duration of brain tissue hypoxia (brain tissue PO2 < 20 mmHg) in hyperoxia-treated groups versus control will be analyzed. Full details of the models and assumptions associated with each may be found in the HOBIT Statistical Analysis Plan.

Secondary Efficacy Analysis. Secondary Analyses:

A series of secondary analysis models have been defined in the statistical analysis plan to evaluate the relationship of HBO treatment to the observed brain tissue PO2, ICP elevation, and amount of corrective treatment received as measured by therapeutic intensity level (TIL) scores. Broadly, the models will seek to answer whether treatment with hyperbaric oxygen prevents brain tissue hypoxia, better controls the level of ICP elevation, leads to less ancillary intervention during care, and whether peak brain tissue oxygen during HBO treatment is associated with improved outcomes at 6 months.

Software and Computations. Computations were performed using software: Fixed

and Adaptive Clinical Trial Simulator (FACTS) (Berry 2010). FACTS is a software program designed to rapidly design, compare, and simulate both fixed and adaptive trial designs. It is built on compiled low-level languages such as Fortran and C++, it is very fast. The simulations take into account all of the testing that is done at each of the interim analysis and are accounted and tallied in the chances of stopping early or late. The scenario where the effect of novel treatment is none (see below) is where we tally the false positives under the null hypothesis which is the Type I error. We changed the early and late stopping rules for success to achieve an acceptable Type I error rate of approximately 20%.

Handling of Missing Data

Under the ITT principle, all subjects who are randomized are included in the analysis. Therefore, missing data, especially in the outcome measure, can be problematic. Extensive efforts will be made to keep all

missing data, particularly the 6 month GOS-E assessment, to a minimum and minimize loss to follow-up. However, it is likely that there will be some missing data. As our primary approach to handling missing data, we will use multiple imputation from a Bayesian hierarchical model. The specific imputation model and secondary sensitivity analyses are defined in HOBIT Statistical Analysis Plan.

9.4 SAFETY ANALYSES

Mortality at 30 days and at 3 and 6 months

For the final analysis of the primary safety outcome, Bayesian survival curves will be generated for deaths from any cause within 30 days and at 3 and 6 months.

Safety Monitoring

The review of safety data will focus on the following adverse events potentially caused by HBO treatment. This subject population presents with significant morbidity with respect to all of the below adverse events; as such it is important to evaluate the presence of events with respect to temporal relationship to treatment (i.e. novel onset or worsening) as well as its relationship across doses. The below table provides the most common adverse events, as well as the expected temporal and dose relationship:

Adverse Event	Clinical Relevance
Pneumothorax Induced by HBO therapy	Abnormal collection of air in the pleural space between the lung and the chest wall, can result in steadily worsening oxygen supply. This is a pressure related phenomena that can also be caused by major trauma or medical procedure. As an AE it is expected to increase as a function of dose atmospheres, but not duration of exposure or number of days treatment (i.e. treatment specific or cumulative OTUs). This is expected to occur during the dive and result in aborting the treatment.

Г	1
Signs of Pulmonary Dysfunction	Signs of pulmonary dysfunction, including PaO2/FiO2 ≤ 200 or requiring PEEP > 10 cm of water to maintain a PaO2/FiO2 ratio of > 200. This is an adverse event which is related to total oxygen toxicity exposure and as such should increase with dose and number of treatments. Symptoms are expected to progressively worsen over subsequent dives.
Pneumonia	This is an adverse event which is related to total oxygen toxicity exposure and as such should increase with dose and number of treatments. Symptoms are expected to progressively worsen over subsequent dives.
Critical decreased CPP (<60 mmHg)	This AE is not specific to HBO therapy, but related to poor outcome (reperfusion). It is expected to be the same in all groups but could demonstrate differences if the process of transferring to the dive chamber causes increased AEs. This should be analyzed as active vs. control.
Critical hypotension (MAP<70 mmHg)	This AE is not specific to HBO therapy, but related to transfer from critical care unit (e.g. disconnecting and reconnecting of lines). It is expected to be the same in all groups but could demonstrate differences if the process of transferring to the dive chamber causes increased AEs. This should be analyzed as active vs. control.
Seizures during HBO treatment	These are expected to occur immediately proximal to treatment as a function of dose oxygen toxicity (rather than cumulative exposure). It is possible to have multiple episodes of AE. Subjects with a baseline propensity to seize may elevate the numerator for this AE.

Hypercarbia during transportation (PaCO2>45 mmHg)	This AE is not specific to HBO therapy, but related to transfer from critical care unit (e.g. disconnecting and reconnecting of lines). It is expected to be the same in all groups but could demonstrate differences if the process of transferring to the dive chamber causes increased AEs. This should be analyzed as active vs. control.
---	---

All AEs and SAEs are summarized by preferred term and associated system-organ class according to the MedDRA adverse reaction dictionary and by treatment group in terms of frequency of the event, number of subjects having the event, time relative to randomization, severity, and relatedness to the treatment. Cumulative incidences of the specific SAEs related to HBO, as well as all SAEs, will be compared across arms. Additional evaluation of safety events will be conducted adjusting for relative baseline co-variants, such as age at baseline and GCS score.

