2.3.3 Assessment of Potential Risks and Benefits

Safety Record for Hyperoxia Treatment. An exemplary safety record for HBO treatment has been demonstrated over the course of four clinical trials at the Hennepin County Medical Center (Gossett 2010, Rockswold 1992, Rockswold 2001, Rockswold 2010, Rockswold 2013). There were 1,984 HBO treatments delivered to 167 subjects with no permanent complications related to the HBO treatment and no subject emergently evacuated from the chamber. In August 2015, the Food and Drug Administration (FDA) gave the HOBIT Trial a "Study May Proceed" notification. All SAEs for our four clinical trials were presented for the FDA review. All of the HBO chambers at our enrolling sites have been granted an investigational device exemption (IDE) and certified for safety by the FDA. Overall, there are four essential factors in maintaining the safety of the severe TBI subject during HBO treatment. First is that the inclusion/exclusion criteria for the subject's respiratory status must meet the criteria outlined in the protocol. Second, it is essential that the same level of care provided in the ICU be continued throughout the subject's transport to and from the HBO chamber (Weaver

1999). Third, the HBO chamber and its environment must become an extension of the ICU. Expertise of appropriate personnel must be as readily available in the HBO environment as it is in the ICU. Unlike the ICUs where the subjects may be left unattended for brief periods of time, the subject is under the constant observation and supervision by several staff members during the HBO treatment. Fourth, the safe application of HBO requires an additional set of skills, knowledge base, and experience that are unique to hyperbaric medicine and essential to the subject and staff safety. A well trained staff of hyperbaric nurses and technicians working under the supervision of a qualified HBO physician, each of whom have a thorough knowledge of the procedures and physiology of HBO therapy, is required. All clinical sites participating in the HOBIT Trial have a team of trained personnel who are aware and fully capable of carrying out these critical procedures.

The subjects receiving NBH (100% FiO2 at 1 ATA) will remain in the ICU to receive their treatments. There would be no increased risk of AEs compared to controls (standard treatment) other than the potential of O2 toxicity.

30	3 OBJECTIVES AND ENDPOINTS							

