OB.	JECTIVES	ENDPOINTS	JUSTIFICATION FOR ENDPOINTS					
Prir	mary							
effe par pro	definitively determine the most ective hyperbaric oxygen therapy radigm and to predict the obability that this treatment will ult in a successful Phase III trial.	Proportion of subjects with favorable outcome at 6-months (Severity adjusted GOS-E)	GOS-E is the most frequently used functional outcome measure for TBI studies.					
Sec	condary							
1.	Determine the effect of HBO treatment on the duration of ICP elevation.	The level and duration of intracranial hypertension (ICP>22 mmHg) will be measured.	Intracranial hypertension is the leading cause of death and deterioration in the first week following TBI (Jull, 2000).					
2.	Determine the effect of HBO treatment on therapeutic intensity level (TIL) scores for controlling intracranial pressure (ICP).	Therapeutic intensity level (TIL) scores. This documents the level of therapies used to control ICP and will be tracked daily during the treatment period.	TIL scores will quantify the intensity of treatment required to control ICP between treatment groups.					
3.	Determine the effect of HBO treatment on brain tissue partial pressure of oxygen (PO2)monitoring.	The level and duration of brain tissue hypoxia (brain tissue PO2 <20 mmHg).	Brain tissue PO2 levels <20mmHg correlate with poor outcome in severe TBI (VanDen Brink, 2000).					
4.	Compare the type and incidence of SAEs between hyperoxia treatment arms and control.	SAEs include: Pneumothorax secondary to HBO, pulmonary dysfunction defined as PaO2/FiO2 (PF) ratio<200, pneumonia, and seizures during HBO.	Special scrutiny is required for complications related to hyperoxia treatment.					

5.	Estimate the effect of peak brain tissue PO2 during hyperbaric oxygen treatment on GOS-E at 6-months.	Dichotomized GOS-E.	Level of O2 achieved in the brain during HBO treatment may correlate with outcome.

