4 STUDY DESIGN

4.1 OVERALL DESIGN

This trial is designed as multicenter, prospective, randomized, adaptive phase II clinical trial. All individuals presenting at an enrolling site with a severe TBI defined as a GCS score of 3-8 (age 16 to 65 years) are initially eligible for inclusion. Subjects with a GCS score of 7 or 8 and a Marshall CT score of 1, as well as subjects with a GCS score of 3 and bilaterally mid position, non-reactive pupils will be excluded. No exclusion criteria will be based on race, ethnicity, or gender. The trial design is adaptive. The primary outcome is a sliding dichotomized adjusted GOS-E at 6 months. However, clinical data from *Baseline*, Day 30, and Day 90 will be used to predict 6-month data. The trial will explore *seven* different active treatment arms for relative efficacy in comparison to the control arm. *Four* pressures (*1.0*, 1.5, 2.0 and 2.5 ATA) and HBO with or without NBH will be studied. *NBH will also be evaluated without HBO, serving both as a treatment arm and a control for the effect of pressure.* Utilizing *the most promising* treatment arm demonstrating improvement in outcome in a subsequent phase III trial will be calculated. *If the probability is > 50%, this treatment arm will be compared for superiority to the control in a future phase III trial.* The maximum number of subjects to be randomized is 200.

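### Section 9.4 tests harm from chamber transport as active versus control, although the active NBH arm is never transported; objective 4 names two events that cannot occur in control

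*Protocol*

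**What the plan says.** Protocol section 9.4 lists adverse events for focused review. For three of them (CPP below 60 mmHg, MAP below 70 mmHg, and the row that begins "Hypercarbia during transportation (PaCO2>45 mmHg") it gives one reason why groups might differ, the move to the chamber, and then fixes the analysis: they "could demonstrate differences if the process of transferring to the dive chamber causes increased AEs. This should be analyzed as active vs. control".

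Section 4.1 refers to seven "different active treatment arms for relative efficacy in comparison to the control arm". NBH alone is one of the seven and is described there as "serving both as a treatment arm and a control for the effect of pressure". Section 2.3.3 states: "The subjects receiving NBH (100% FiO2 at 1 ATA) will remain in the ICU to receive their treatments". It adds: "There would be no increased risk of AEs compared to controls (standard treatment) other than the potential of O2 toxicity". Section 6.3, under Blinding, says that an outcome difference caused by transport should be attributed to the HBO group alone.

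Secondary objective 4 in section 3 compares SAEs between the hyperoxia arms and control. Its endpoint column reads: "SAEs include: Pneumothorax secondary to HBO, pulmonary dysfunction defined as PaO2/FiO2 (PF) ratio<200, pneumonia, and seizures during HBO".

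**The concern.** A contrast meant to detect harm from transport should separate transported from untransported subjects. Active versus control does not. It adds to the exposed group an arm that is never moved and that the protocol expects to match control apart from oxygen toxicity. The resulting bias is toward finding no harm, which is the less safe direction for a safety analysis. The instruction in 9.4 also cannot be squared with section 6.3.

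The concern about objective 4 is of a different kind. Two of its named events include exposure to HBO in their definition. Control and NBH subjects can never have them, so comparing those two events with control does not measure excess risk.

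**Working it through.** **1. Is NBH an active arm?** Section 6.3 gives a burn-in of 56 subjects: 11 control, 9 in 2.5 ATA+NBH, and 6 in each other active arm.

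- Seven active arms, NBH included: 11 + 6×6 + 9 = 56, which matches the protocol.
- Six active arms, NBH left out: 11 + 5×6 + 9 = 50, which does not.

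NBH is therefore active, in agreement with section 4.1.

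**2. Dilution.** Let *f* be the NBH share of active subjects. Assume that NBH has the control rate for these events, as section 2.3.3 implies apart from oxygen toxicity. Then

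expected difference, active versus control = (1 − *f*) × true difference, HBO versus control.

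At burn-in, *f* = 6/45 = 13.3%, and 39/45 = 86.7% is retained. After burn-in, allocation follows the probability of being the best arm, so *f* can move. The shares of 25% and 40% below are assumptions, as is the true difference of 20 points.

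| NBH share of active | Retained | A true 20 points appears as |
|---|---|---|
| 13.3% (burn-in) | 86.7% | 17.3 |
| 25% (assumed) | 75% | 15.0 |
| 40% (assumed) | 60% | 12.0 |

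There is an upper limit. With at most 200 subjects, 200 − 56 = 144 follow burn-in. If all of them went to NBH, its share would be (6 + 144)/(200 − 11) = 150/189 = 79%. This is a bound, not a forecast.

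**3. What regrouping gains, as illustration.** The protocol gives no event rates, alpha or power for these contrasts. The figures assume a fixed-sample two-sided 0.05 test and 200 subjects, with control and active in burn-in proportions (200×11/56 ≈ 39 control, 200×45/56 ≈ 161 active).

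| Assumed rates, control vs HBO | NBH share | Active vs control | HBO vs control | HBO vs control + NBH |
|---|---|---|---|---|
| 0.30 vs 0.50 | 13.3% | 0.50 | 0.61 | 0.76 |
| 0.30 vs 0.50 | 40% | 0.27 | 0.57 | 0.83 |
| 0.10 vs 0.25 | 13.3% | 0.43 | 0.53 | 0.70 |
| 0.10 vs 0.25 | 40% | 0.23 | 0.50 | 0.80 |

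Regrouping needs no extra subjects. It removes only the dilution from NBH. HBO subjects too unstable for treatment receive usual care (section 6.2.1), and that dilution stays in any comparison by randomized arm.

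**4. Objective 4.** No arithmetic is needed. A subject who receives no HBO cannot have a pneumothorax secondary to it or a seizure during it. The protocol recognizes background causes: 9.4 names trauma and procedures for pneumothorax, and 6.2.1 says severe TBI subjects are prone to seizures. Pulmonary dysfunction and pneumonia, also listed under objective 4, can occur in every arm.

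**The case against.** The strongest reply is that this is one loose phrase in a monitoring table. Section 9.4 also summarizes all AEs and SAEs by treatment group and compares SAEs across arms, so NBH can be seen on its own. At the only share that follows from the protocol, the dilution is 13%. Exact contrasts and windows are often left to the SAP. The first two points stand and limit the size of the problem. The third does not remove it, because the protocol names a contrast and that contrast conflicts with its own section 6.3.

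A reader might infer more than the text supports:

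- *Background seizures and pneumothoraces in control go uncounted.* They do not. Sections 8.3 and 8.4.4 record all AEs through Day 6 or discharge and SAEs to the end of study, and 9.4 tabulates them by group. In 9.4 itself, the pneumothorax and seizure rows carry no active-versus-control instruction. No risk ratio is planned, so an infinite one is not a planned result.
- *Hypercarbia is zero by definition in control.* Its label points that way, but its row shares the statement "It is expected to be the same in all groups but could demonstrate differences if the process of transferring to the dive chamber causes increased" adverse events, which presumes counting in all groups.
- *Adaptive randomization could take NBH to any share.* The bound is 79% of active subjects.
- *The go/no-go decision rests on these contrasts.* Sections 4.2 and 9.3 tie that support to ICP, TIL and brain tissue PO2, and objective 4 does not name the three transport events.

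**Conclusion.** The point holds in two limited parts.

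First, the active-versus-control contrast for low CPP, hypotension and hypercarbia does not match the mechanism given for it, and it contradicts section 6.3. It understates a transport effect by the NBH share of active subjects: 13.3% at burn-in, and more if NBH is favored later, by an amount the protocol cannot fix. This rests on NBH subjects having the control rate for these events. The power figures rest on assumed rates and shares and show direction only.

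Second, objective 4 sets two HBO-conditional events in a comparison with control, where they cannot occur. The background data needed for a fair comparison are already collected.

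Neither part touches the primary efficacy analysis. Both are worth correcting because the first bias runs against detecting harm and the change is small.

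**What to change.** In section 9.4, replace active versus control for the three events with the six HBO arms versus control plus NBH, by randomized arm and over the same window in every arm. If pooling NBH with control is unwelcome because of possible oxygen toxicity, compare the HBO arms with control and show NBH separately. State what transportation means for hypercarbia in arms that are not moved. Interpret that event with caution or report it descriptively: section 6.2.1 has blood gases checked before dives and, in multiplace chambers, as needed during them, so HBO arms have more chances of detection. Section 8.2 does not name PaCO2 among the monitored variables.

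In objective 4, base the comparison of hyperoxia with control on any pneumothorax and any seizure over a common window, and keep relation to HBO as a descriptive attribute.

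The cost is a change of wording and reprogrammed tables. The schedule in section 1.3 already has hourly monitoring and ventilatory forms on Days 1 to 6 and marks only the study therapy form as non-control; section 8.3 already records the extent and duration of low MAP and low CPP. The downside is that any-cause counts include background events, which adds noise.

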10 SUPPORTING DOCUMENTATION AND OPERATIONAL CONSIDERATIONS

10.1 REGULATORY, ETHICAL, AND STUDY OVERSIGHT CONSIDERATIONS

10.1.1 INFORMED CONSENT AND EXCEPTION FROM INFORMED CONSENT

This protocol and the informed consent document and any subsequent modifications will be reviewed and approved by the Central IRB. Participants will be enrolled in this trial either with the prospective informed consent of a legally authorized representative (LAR) or with exception from informed consent (EFIC) for emergency research under the conditions established at 21CFR50.24. When a potentially eligible subject arrives at the hospital, study teams will work diligently to determine the availability of an LAR. If an LAR is available to participate in an informed consent process within 6 hours of the patient's arrival at the enrolling hospital, then the patient can only be enrolled with the prospective informed consent of the LAR. If no LAR is available at that time, eligible patients may be enrolled with EFIC. Subsequent to an EFIC enrollment, efforts to contact an LAR will continue. An LAR will be notified of an EFIC enrollment, and consent to continue in the study will be sought, at the earliest opportunity.

10.1.1.1 CONSENT/ASSENT AND OTHER INFORMATIONAL DOCUMENTS PROVIDED TO PARTICIPANTS

If a subject is enrolled with informed consent, or using EFIC, a copy of the consent form will be given to the LAR, and this fact will be documented in the subject's record.

10.1.1.2 ENROLLMENT WITH INFORMED CONSENT

Consent is obtained by either the clinical site PI or by individuals to whom the clinical site PI has delegated authority to obtain informed consent. The delegation of authority is documented and maintained in WebDCU[™]. As with most clinical trial responsibilities delegated by the clinical site PI, it is his/her responsibility to ensure that the delegation is made only to those individuals who are qualified to undertake the delegated tasks, and that there is adherence to all applicable regulatory requirements and Good Clinical Practices (GCP) Guidelines. Additionally, it is the investigator's responsibility to ensure that the subject's legally authorized representative (LAR) has been given an adequate explanation of the purpose, methods, risks, potential benefits and subject responsibilities of the study. The consent form must be an up-to-date document that has been approved by the Central institutional review board (CIRB). A signed and dated informed consent is required prior to randomization.

In the HOBIT Trial, all subjects will be comatose, therefore, prospective informed consent will be obtained from a LAR for the subject. Every attempt will be made to contact the subject's family as soon as possible after the subject's admission, and in accordance with the individual hospital's protocol. To the extent possible, consent discussions should be carried out in a private setting without distraction. No coercion will be applied. The LAR and other family members will be provided a verbal description of the trial and all the items described in the consent form will be reviewed and explained. The LAR will be given an opportunity to read the informed consent document, ask and have answered any questions they may have about the study.

